receiving placebo reported dry eye (n=1). All eye disorders AEs were of mild to moderate intensity, resolved spontaneously (without treatment), and were more frequently reported with highest dose (40 mg). Among them, the AEs of blurred vision, photophobia (“Increased ocular light sensitivity”), visual impairment (“distorted contrast perception”, “distorted colour perception”) reported by 8 out of 47 subjects receiving emodepside were considered as treatment-related by the Investigator. Also of note, at the highest dose (40 mg), lightheadedness (n=1), dizziness (n=1) or headache (n=1) were reported concomitantly to blurred vision.

None of the volunteers met any of the protocol-specified withdrawal criteria and overall tolerability to emodepside has been acceptable up to 20 mg. The presence of post-dose visual disturbances in subjects of Cohort 8 receiving either 40 mg solution or placebo may warrant some concern and escalation was stopped at this dose level.

The pharmacokinetic results obtained so far show that T_{max} for the LSF solution is consistently about 1 h post-dose when fasted. Mean C_{max} and AUC for the LSF solution have been roughly dose-proportional, with low to moderate inter-individual variability. The plasma half-life during the first 24 h is very short for a single dose of emodepside. After 3, 7, 16 and 47 h the maximum plasma concentration is reduced to 50%, 25%, 12.5% and 6.25% respectively. Terminal plasma half-life is 523 h. Although data of Cohort 9 (which was treated with a single dose of emodepside with food) are still under review, administration of the LSF of 10 mg with a high fat, high-calorie meal resulted in a clinically relevant food effect with a reduction of AUC to ~67%, C_{max} to 42% and a delay of the T_{max} up to 2.33 h. Therefore, the recommendation of administration of the emodepside (LSF) under fasted conditions is given.

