1.5. Assessment and management of risk

The factors taken into account in the assessment of risk to subjects in this study are as follows:

- The planned daily doses of emodepside have been administered to humans as single doses and were well tolerated. Based on the first-in-human clinical study, overall tolerability to emodepside has been acceptable up to 20 mg. Post-dose visual disturbances were observed more frequently at 40 mg, and although these visual and nervous system disturbances were considered non-serious and mild in intensity, dose escalation was stopped at this dose level. All visual disturbances were transient in nature and resolved spontaneously within 24 h, and without treatment.
- During the study, the dose will be increased only if the PK, safety and tolerability of the previous dose is acceptable and if the investigator and sponsor's medical representative agree that it is appropriate to give a higher dose. The next planned dose level may be reduced, or a dose level may re-tested or an intermediate dose level selected, based on emerging data. The total daily dose will not exceed 20 mg emodepside (as LSF solution at a concentration of 1 mg/mL).
- Subjects will undergo a comprehensive ophthalmology assessment at screening and will be excluded from the study if any ocular pathology is detected. Additional ophthalmology assessments will be performed during the study, if clinically indicated.
- Subjects will undergo a full neurological assessment at screening, Day 0 and at discharge from the ward in order to detect and assess any neurological disorder or change.
- In the first-in-human trial (DNDI-EMO-01), emodepside was shown to undergo bi-phasic elimination with a dominant half-life ($t_{1/2\ 0-24}$) estimated at approximately 11 h, and terminal half-life ($t_{1/2\ 0-\infty}$) over 520 h. In order to comprehensively assess safety parameters over this period, volunteers will be followed up until Day 120.

2. Study Objectives and Endpoints

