$\%AUC_{extrap}$	Percentage of AUC_{∞} extrapolated from from t_{last} to infinity, using the following formula
	$\%AUC_{extrap} = \frac{100 \times AUC_{t-\infty}}{AUC_{\infty}}$
$C_{max,ss}$	The observed maximum plasma concentration measured in a subject at steady state, identified by inspection of the drug concentration vs. time data.
$C_{max,ss}/D$	The observed maximum plasma concentration measured in a

	subject at steady state, identified by inspection of the drug concentration vs. time data, corrected for dose.
$C_{\max,ss,norm}$	The observed maximum plasma concentration at steady state, corrected by dose and body weight
t_{\max}	The time at which C_{\max} was apparent, identified by inspection of the drug concentration vs. time data.
MRT_{∞}	The mean residence time extrapolated to infinity
CL_{ss}/F	Apparent total clearance from plasma at steady state will be calculated using the following formula:

$$CL_{ss} / F = \frac{Dose}{AUC_{\infty}}$$

V_z/F	Apparent volume of distribution will be calculated at steady state using the following formula:
---------	---

$$V_z / F = \frac{Dose}{\lambda_z \bullet AUC_{\infty}}$$

$RA(C_{\max})$	Accumulation ratio for C_{\max} , calculated from C_{\max} at steady state and C_{\max} after single dose
$RA(AUC_{\tau})$	Accumulation ratio for AUC_{τ} , calculated from AUC_{τ} at steady state and AUC_t after single dose, where $t = \tau$.

Steady state (days 1 – 9)

C_{trough}	Trough plasma concentration (measured concentration at the end of a dosing interval at steady state [taken directly before next administration]) obtained directly from the concentration-time data.
---------------------	--

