3.1.2 Multiple Dose

Emodepside parameters to be calculated on Day 9.

Text Symbol	Definition	Calculation	Typical Units	Log Transform	WNL	CDISC Controlled Terminology	TFL Symbol
Concentrations during and after multiple dosing							
C_{trough}	Trough plasma concentration	Trough plasma concentration (measured concentration at the end of a dosing interval at steady state [taken directly before next administration]) obtained directly from the concentration-time data.	ng/mL	Y	-	CTROUGH	C_{trough}
Concentrations and times (after final dose)							
$C_{\text{max,ss}}$	Maximum (peak) plasma concentration at steady state	The maximum (peak) plasma concentration will be obtained directly from the concentration-time data.	ng/mL	Y	Cmax	CMAX	$C_{\text{max,ss}}$
$C_{\text{max,ss}}/\text{Dose}$	Dose-normalised C_{max} at steady state	The dose-normalised C_{max} will be calculated as $C_{\text{max}}/\text{Dose}$ administered	(ng/mL)/mg	Y	Cmax_D	CMAXD	$C_{\text{max,ss}}/D$
$C_{\text{max,ss,norm}}$	Observed maximum plasma concentration corrected by dose and body weight at steady state	The C_{max} normalised by dose and body weight will be calculated as $C_{\text{max}}/(\text{Dose administered} * \text{body weight})$	(ng/mL)/(mg*kg)	Y	-	CMAXWD	$C_{\text{max,ss,norm}}$
t_{max}	Time to reach maximum (peak) plasma concentration	The first time of maximum (peak) plasma concentration will be obtained directly from the concentration-time data.	h	N	Tmax	TMAX	t_{max}
Half-life (after final dose)							
λ_z	Terminal rate constant	The apparent terminal phase rate-constant (λ_z) will be estimated by linear regression of logarithmically transformed concentration versus time data.	1/h	Y	Lambda_z	LAMZ	λ_z
$t_{1/2}$	Terminal half-life	The terminal half-life calculated from the terminal slope of the log concentration-time curve, as follows: $t_{1/2} = \frac{\log_e 2}{\lambda_z}$	h	Y	HL_Lambda_z	LAMZHL	$t_{1/2}$
$t_{1/2,\text{dom}}$	Dominant half-life	The dominant half-life calculated from the terminal slope of the log concentration-time (0-24h) curve, as follows:	h	Y	HL_Lambda_z	LAMZHLD	$t_{1/2,0-24}$

Text Symbol	Definition	Calculation	Typical Units	Log Transform	WNL	CDISC Controlled Terminology	TFL Symbol
		$t_{1/2, dom} = \frac{\log_e 2}{\lambda_z}$					
Areas under the curve (after final dose)							

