MRT _∞	Mean Residence Time extrapolated to infinity	The mean residence time will be calculated using: $MRT = \frac{AUMC}{AUC_{\infty}}$	h	Y	MRTINF_pred	MRTEVIFP	MRT _∞
Accumulation and time invariance ratios							
R _{ac} (AUC _t)	Accumulation ratio for AUC	Accumulation ratio will be calculated from AUC _t at steady state and AUC _t after single dose	-	N	-	ARAUC	R _{ac} (AUC _t)
R _{ac} (C _{max})	Accumulation ratio for C _{max}	Accumulation ratio will be calculated from C _{max} at steady state and C _{max} after single dose	-	N	-	ARCMAX	R _{ac} (C _{max})

* Calculated only for Cohort 3

**Calculated only for Cohorts 1 and 2

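### Cmax,ss, Ctrough and the accumulation ratios are defined as steady-state quantities, but with a 523 h terminal half-life 10 days of dosing does not reach steady state; they should be defined as Day 9 (10-day) values.

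*Protocol*

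**What the plan says.** Protocol 8.4.2 places Ctrough under a heading that declares Days 1 to 9 to be steady state, and defines it as the "measured concentration at the end of a dosing interval at steady state". Cmax,ss is "The observed maximum plasma concentration measured in a subject at steady state". RA(Cmax) and RA(AUCtau) are each a steady-state value over a single-dose value.

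SAP Appendix B 3.1.2 keeps these meanings. Cmax,ss is the "Maximum (peak) plasma concentration at steady state", and for both ratios "Accumulation ratio will be calculated from" the steady-state value and the single-dose value. The SAP groups Ctrough under concentrations during and after multiple dosing, but its definition still refers to steady state.

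Protocol 1.4 says: "Terminal plasma half-life is 523 h". For the earlier decline it says: "After 3, 7, 16 and 47 h the maximum plasma concentration is reduced to 50%, 25%, 12.5% and 6.25% respectively". Protocol 1.5 adds that "emodepside was shown to undergo bi-phasic elimination with a dominant half-life" of about 11 h over the first 24 h, and a terminal half-life above 520 h. Dosing runs from Day 0 to Day 9: ten once-daily doses in Cohorts 1 and 2, and 19 twice-daily doses in Cohort 3.

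**The concern.** Named secondary PK endpoints carry a property that the design does not give them. One conflict needs no model. In Cohorts 1 and 2 the Day 1 pre-dose sample follows a single dose. Day 0 sampling stops at 15 h, so this is also the only planned sample at 24 h for the single-dose AUC24. The protocol therefore treats one sample as both single-dose and steady-state.

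At stake is what the trial can say about accumulation. A ratio defined against steady state invites the reader to take it as complete. The interim after Cohorts 1 and 2 (protocol 10.1, SAP 7.1) is meant to inform progression to later phases, and there the difference between 10-day and full accumulation would matter.

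**Working it through.** Neither document states a fraction of plateau or a time to steady state, so there is no plan figure to reproduce. The check builds one from the protocol's own numbers.

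**Inputs (protocol 1.4 and 7.1).** Terminal half-life 523 h; 50, 25, 12.5 and 6.25% of Cmax at 3, 7, 16 and 47 h; Tmax "for the LSF solution is consistently about 1 h post-dose when fasted"; tau = 24 h with 10 doses, or tau = 12 h with 19 doses. Mean Cmax and AUC are described as roughly dose-proportional, which supports superposition.

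**Step 1: the slow phase alone.**
- Position of the last dose: 216/523 = 0.41 half-life.
- Fraction of plateau: 1 − 2^(−216/523) = 25%; at 240 h, 1 − 2^(−240/523) = 27%.
- Time to 90%: 523 × log2(10) = 1,737 h, about 72 days. This is arithmetic only, not a suggestion on duration.

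**Step 2: single-dose curve.** With s = hours after Tmax and a linear rise over the first hour, C = A·2^(−s/h1) + B·2^(−s/h2) + G·2^(−s/523). This was fitted exactly through the quoted points. The text does not say whether the times run from dosing or from Tmax, so both were used.

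| Times counted from | A | B | G | h1 (h) | h2 (h) |
|---|---|---|---|---|---|
| Dosing | 0.587 | 0.348 | 0.0646 | 1.06 | 6.00 |
| Tmax | 0.818 | 0.143 | 0.0387 | 2.31 | 19.1 |

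**Step 3: superposition.** The Day 9 profile is the sum of C(t + k·tau) over k = 0 to 9 (once daily) or 0 to 18 (twice daily). Plateau is the same sum without limit.

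By hand for the once-daily pre-dose trough on Day 9, times from dosing:
- r = 2^(−24/523) = 0.9687.
- Slow phase: 0.0647 × r(1 − r^9)/(1 − r) = 0.0647 × 7.70 = 0.498. Here 0.0647 is 0.0646 × 2^(1/523).
- Slow phase at plateau: 0.0647 × 30.94 = 2.002.
- The 6 h phase adds 0.026 to each.
- Ratio: 0.524/2.028 = 26%.

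| Day 9 as % of plateau | Once daily | Twice daily |
|---|---|---|
| Ctrough (pre-dose) | 26–31 | 27–33 |
| AUCtau | 33–42 | 32–41 |
| Cmax | 50–61 | 41–51 |

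| Ratio to Day 0 | Day 9 | Plateau |
|---|---|---|
| RA(AUCtau), once daily | 2.4–3.1 | 5.7–9.4 |
| RA(AUCtau), twice daily | 3.0–4.0 | 7.5–12.4 |
| RA(Cmax), once daily | 1.4–1.5 | 2.3–3.0 |
| RA(Cmax), twice daily | 1.9–2.1 | 3.7–5.1 |

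On these curves the Day 1 trough is 4–10% of plateau. Troughs still rise on average 8–13% per day over Days 5–9.

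**Step 4: sensitivity to the tail.** The documents give no concentration after 47 h, so the weight of the 523 h phase is an assumption. Two lower-tail cases were tried: 1.5% of Cmax at 168 h and 523 h thereafter, and an 11 h/523 h model with a 2% slow share. Trough then reaches 44–57%, AUCtau 55–65% and Cmax 67–76% of plateau. No case that kept a 523 h phase came near 90%.

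**Scale check.** The fitted AUC0–24 × 612 ng/mL is 3,469–3,881 ng·h/mL, against the 4,315 quoted for 40 mg, so it is 10–20% low. The type of that AUC is not stated. The fitted 523 h tail alone would add G × (523/ln 2) × 612, about 17,900–29,800, so on these curves 4,315 is not an AUC to infinity. It does not settle the weight of the tail.

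**The case against.** The strongest reply is that this is a matter of labels. The endpoint lists tie the values to Day 9 and the troughs to Days 1–9, the SAP table is headed as Day 9 parameters, and the Day 9 AUC12 and AUC24 carry no steady-state label. All of this is correct. A reader might infer that the reported Day 9 numbers will themselves be biased low. The documents do not support that: the measured maxima, troughs and ratios describe 10 days of dosing correctly.

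A reader might also infer that nothing planned would expose the problem. That goes too far. SAP 15.1.1 and 18.1 plan concentration summaries by time point and individual and geometric-mean plots, and the terminal half-life is derived. Rising troughs would be visible, though no analysis formally assesses them.

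A third inference is that the ratios will be used to project longer dosing. Neither document does so. The PK stopping rule uses predicted mean Cmax at the next dose level, and protocol 3.1 says the duration reflects single-dose modelling and the anticipated length of treatment. But it does not say that the modelling predicts steady state by Day 9.

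The 11 h dominant half-life does not rescue the label. Taken alone it would give more than 99.9% of plateau by Day 9, but it describes only the first 24 h, and a 523 h phase follows.

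**Conclusion.** The point holds as a mismatch between definition and design. Cmax,ss, Ctrough and both accumulation ratios are defined at a steady state that 10 days of dosing does not reach. The values stand as 10-day results; only their reading as plateau exposure or full accumulation is too low.

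The direction is firm given the 523 h half-life, but the size is not. Read as plateau values, Day 9 AUCtau would be low by a factor of about 2.4–3.1 on the fitted curves (1/0.42 to 1/0.32), and by about 1.5–1.8 in the lower-tail cases (1/0.65 to 1/0.55). These figures rest on linear kinetics, preliminary single-dose means and an assumed tail beyond 47 h. They should not be quoted as one range across parameters, because trough, AUCtau and Cmax approach plateau at different rates.

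**What to change.** In protocol 8.4.2 and SAP Appendix B 3.1.2, and in the endpoint lists that use the same names:

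- Rename Cmax,ss and its dose-corrected and dose-and-weight-corrected forms to Cmax (Day 9).
- Remove steady state from the Ctrough definition and from the protocol heading over it, and report troughs by day.
- Define RA(Cmax) and RA(AUCtau) as Day 9/Day 0 ratios, described as 10-day accumulation.
- Add one table: the geometric mean daily ratio of Ctrough over Days 5–9 (from each subject's slope of log Ctrough on day) with its 95% CI, by dose. The pre-dose samples are already planned. A ratio above 1 shows continuing accumulation; an interval that includes 1 does not demonstrate steady state.
- State that plateau is not claimed, and label any plateau value as a model prediction with its assumptions.

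The cost is wording in two documents and one small table, with no new samples or subjects. The table will be imprecise with six subjects per dose, and accumulation will be reported openly as incomplete.

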8.4.3. PD assessments

Blood samples for the determination of levels of glucose, insulin, glucagon and cortisol, and prolactin and leptin (Days –1 and 9 only) will be collected from each subject during the study, at the time points indicated in the Schedule of events (Section 5). In addition, glucose and insulin measurements will be used in the OGTT on Days –2, 1, 8 and 120.

The exact date and time of sampling will be recorded in the CRF. Blood volumes for those samples are shown in Section 8.4.4.

Collection of samples for pharmacodynamic assessments: Blood for glucose, insulin, cortisol, prolactin and leptin will be collected in serum-separating tubes (SST) with a gelatin plug. Samples will then be transferred to the laboratory.

8.4.4. Total blood volume

The blood volume planned to be collected from each subject during the course of this study is detailed in Table 4 . Additional samples may be required in the event of AEs. The total blood volume to be taken during the study will be 538.5 mL.

Additional blood may need to be collected for assay of emodepside, its metabolites, or for laboratory safety tests. No more than an extra 50 mL blood will be taken.

After collection, samples (blood and urine) may be stored for up to approximately 12 months after end of study before being destroyed.

Table 4 . Blood volumes for Cohorts 1–3

Test	Planned number of tests	Volume (mL)	Total planned blood volume (mL)
Haematology	14	2	28
Hb1Ac	2	2	4
Biochemistry including free T3 and T4, and glucose	40	2.5	100
Coagulation	14	3	42
Serology	1	2.5	2.5
Insulin, cortisol and prolactin	23	2.5	57.5
Glucagon	22	2	44
Leptin	2	2.5	5
Emodepside PK ^a	45	3	135
Metabolites of emodepside	26	5	130
Total			548 mL

^a optional samples can be taken from PK blood collections in up to 3 cohorts, to cover a whole PK profile. Those samples may be retained for possible future bioanalytical method development. No additional blood will be collected for those optional samples.

After each blood sample, the cannula will be flushed with 3–5 mL normal saline, to keep it patent. In order to minimise dilution of each subsequent blood sample with normal saline, the following procedure will be used: about 2 mL will be drawn via the cannula into the sampling syringe, and immediately re-injected gently via the cannula. The definitive blood sample will be taken after a 10-second delay.

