5.1. Table 2: Schedule of events overview

Procedure	Screening		Day (s)											Follow-up (Day 30 ±2 Days)	Long-term follow-up visits (Days 60, 90, and 120 ±2 Days) ¹⁸	
	Day -28 to -3		-3	-2	-1	0	1	2-8	9	10-14	17 (±2)	20 (±2)	23 (±2)			27 (±2)
	Visit 1	Visit 2														
Subject demographics and informed consent	X															
Inclusion/Exclusion Criteria	X					X										
Medical history	X															
Inpatient stay			←—————→													X
Outpatient visit	X	X									X	X	X	X	X	X
Drugs of abuse screen and alcohol breath test ¹	X		X													X
Full physical examination ²	X						X		X					X		
Short physical examination ²					X	X	X	X	X	X	X	X	X	X		X
Full neurological examination ³	X					X				X						
Short neurological examination ⁴					X	X	X	X	X	X	X	X	X	X	X	X
Ophthalmological examination ⁵	X	X								X						
Oral Glucose Tolerance Test (OGTT) ⁶				X			X	X								X
Glucose, insulin, glucagon and cortisol ⁷					X	X	X		X	X				X		
Administration of emodepside ⁸						X	X	X	X							
12-lead safety ECGs ⁹	X				X	X	X	X	X	X				X		

5. Ophthalmological examination will be performed at the second screening visit after all other eligibility criteria have been met, and on Day 10. If deemed necessary by the ophthalmologist, additional ophthalmology follow-up visit(s) may be scheduled for eye-related AEs. Subjects will be given the Ishihara test at screening visit 1.
6. Blood samples taken for glucose and insulin measurement will be used to complete an Oral Glucose Tolerance Test (OGTT). Samples taken will be:
- on Day -2: at -48, -47, -46 and -44 h before the morning dose on Day 0
 - on Day 1: before and at 1, 2 and 4 h after the morning dose
 - on Day 8: before and at 1, 2 and 4 h after the morning dose
 - on Day 120 at 0, 1, 2 and 4 h timepoints relative to dosing
- Subjects will fast until completion of the OGTT test; lunch will be provided immediately afterwards
7. Blood samples for measurement of glucose, insulin, glucagon and cortisol will be taken:
- on Day -1: at -24, -23, -22, -20 and -12 h before the morning dose on Day 0
 - on Day 0: before and at 1, 2, 4 and 12 h after the morning dose
 - on Day 1: before the morning dose
 - on Day 9: before and at the following time points after the morning dose: 1, 2, 4, 12, 24 (Day 10), 48 (Day 11), 72 (Day 12), 96 (Day 13) and 120 h (Day 14); and at follow up (Day 30 (\pm 2 days)). Subjects will fast for the Day 11, 12, 13, 14 and 30 time points.

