8.4. Assessments

8.4.1. Sampling time points and additional tests

With the Sponsor's approval, additional time points may be introduced, and changes to time points may be made, if there is reason to believe that the change might improve the quality of the data (for example, if it is believed that an important effect of emodepside is occurring at a time when no measurements are scheduled), or if extra procedures are needed in the interest of subject safety. However, the total volume of blood taken in the trial will not exceed the value given in Section 8.4.4, unless in the opinion of the Investigator, it's in the subject's best interest that extra blood is taken for additional safety tests.

An additional 48 h' residence on the ward, and additional outpatient visits, will be permitted in the event of a technical failure, and/or if extra observations or samples of

blood are needed.

In the case of any samples for pharmacokinetic analysis, the following will not be regarded as protocol deviations:

- Deviations of not more than 5 min on measurements scheduled up to and including 4 h after a morning dose;
- Deviations of not more than 15 min on measurements scheduled from after 4 h to 24 h after a morning dose;
- Deviations of not more than 1 h on measurements scheduled more than 24 h after a morning dose; and
- Deviations of not more than 2 days on measurements scheduled for outpatient visits, the Follow-up visit, and long-term follow-up visits.

For all other procedures, the following will not be regarded as protocol deviations:

Table 7. Permitted deviation windows for all other procedures¹

Time point		Deviation window in relation to the scheduled time point
Day -1	Days 0-9	
Pre -24 h	Pre-dose (0 h)	Within 75 min before
-24 h to -23.5 h	Up to and including 30 min after the morning dose	± 5 min
After -23.5 h to -20 h	After 30 min to 4 h after the morning dose	± 10 min
After -20 to -12 h	After 4 h to 24 h after the morning dose	± 15 min
NA	more than 24 h after the morning dose	± 1 hour ²

1. Urine collection for laboratory safety tests will be within 2 h of the scheduled time point and all pre-dose urine samples will be collected pre-dose.
2. Deviations at outpatients visits (during Days 15 to 30) are ± 2 days, as shown in the in Schedule of events (Section 5)

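### Protocol 8.4.4 states 538.5 mL of blood, but its own table sums to 548 mL and does not match the schedule, so the ceiling in 8.4.1 is unclear

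*Protocol*

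**What the plan says.** Protocol 8.4.4 gives the total twice. The text reads "The total blood volume to be taken during the study will be 538.5 mL"; the blood-volume table directly below prints 548 mL. The same section allows for additional blood for emodepside, metabolite or laboratory safety assays: "No more than an extra 50 mL blood will be taken".

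Protocol 8.4.1 lets the Sponsor approve added or changed time points, provided that "the total volume of blood taken in the trial will not exceed the value given in Section 8.4.4". The exception is extra blood for additional safety tests that the Investigator judges to be in the subject's best interest.

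Two table rows matter most: "Biochemistry including free T3 and T4, and glucose" (40 tests at 2.5 mL) and "Insulin, cortisol and prolactin" (23 tests at 2.5 mL). Leptin has its own row (2 tests at 2.5 mL).

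On the schedule side, section 8.4.3 says that "glucose and insulin measurements will be used in the OGTT on Days –2, 1, 8 and 120". Footnote 6 to the schedule in section 5.1 gives four samples on each of those days, including "on Day 120 at 0, 1, 2 and 4 h timepoints relative to dosing". Footnote 7 lists the glucose, insulin, glucagon and cortisol profile. It also says that leptin and prolactin, at Screening Visit 1 and Day 9, come from the insulin sample.

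**The concern.** One section gives one quantity two values, and another section makes that quantity a limit. If the limit is 538.5 mL, a subject sampled exactly as the table plans is above it. If it is 548 mL, the sentence stating the total is wrong. A site asked to add a time point under 8.4.1 cannot tell how much room it has.

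Choosing the table's figure does not settle the matter, because the table's counts differ from the schedule in both directions: some scheduled samples have no tube, and leptin may be charged twice. What is at stake is an operative limit on blood drawn from healthy volunteers. No endpoint, power or analysis depends on it.

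**Working it through.** **Step 1. The table's own sum (tests × mL, protocol 8.4.4).**

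| Row | Tests × mL | mL |
|---|---|---|
| Haematology | 14 × 2 | 28 |
| HbA1c | 2 × 2 | 4 |
| Biochemistry and glucose | 40 × 2.5 | 100 |
| Coagulation | 14 × 3 | 42 |
| Serology | 1 × 2.5 | 2.5 |
| Insulin, cortisol, prolactin | 23 × 2.5 | 57.5 |
| Glucagon | 22 × 2 | 44 |
| Leptin | 2 × 2.5 | 5 |
| Emodepside PK | 45 × 3 | 135 |
| Metabolites | 26 × 5 | 130 |
| **Sum** | | **548** |

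The printed 548 mL is reproduced. The text figure is not: 548 − 538.5 = 9.5 mL, or 9.5 / 538.5 = 1.8%.

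**Step 2. Times in the schedule footnotes (section 5.1).**

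- Safety laboratory (footnote 15): screening; Days −1, 0, 1, 5, 8, 9, 10, 14, 23, 30, 60, 90, 120 = 14.
- PD profile (footnote 7): 5 on Day −1, 5 on Day 0, 1 on Day 1, 10 from Day 9 to Day 14, 1 on Day 30 = 22.
- OGTT (footnote 6): 4 days × 4 = 16.

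The haematology, coagulation and glucagon rows agree with these counts. Emodepside PK also agrees: 13 (Day 0) + 8 (Days 1–8) + 19 (Day 9 onwards) + 5 (outpatient and Day 30) = 45. So do metabolites: 13 + 13 = 26.

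**Step 3. Biochemistry and glucose row.** Count each coinciding time once.

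- Laboratory and profile times coincide on seven occasions (Days −1, 0, 1, 9, 10, 14, 30): 14 + 22 − 7 = 29.
- Three OGTT times are already in that set (first sample on Days 1, 8 and 120), leaving 16 − 3 = 13.
- Total 29 + 13 = 42, against 40 in the table. Shortfall: 2 × 2.5 = 5 mL.

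Without sharing, the count would be 14 + 22 + 16 = 52. The table's 40 therefore already presumes sharing, and 42 is the minimum. A row of 40 must include at least 40 − 29 = 11 OGTT draws.

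**Step 4. Insulin row.** The table's 23 equals the 22 profile times plus the screening prolactin sample. Only the Day 1 pre-dose OGTT time coincides with the profile, so the OGTT adds 16 − 1 = 15 insulin times. The scheduled count is 23 + 15 = 38. Separate tubes for the additional times would take 15 × 2.5 = 37.5 mL.

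**Step 5. Leptin row.** The table charges 2 × 2.5 = 5 mL. If leptin comes from the insulin sample, as footnote 7 says, that 5 mL is not drawn.

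**Step 6. Totals, starting from 548 + 5 = 553 mL.**

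| OGTT insulin | Leptin | Calculation | mL |
|---|---|---|---|
| Shares glucose tube | Shares insulin tube | 553 − 5 | 548 |
| Shares glucose tube | Own tube | 553 | 553 |
| Own tube | Shares insulin tube | 553 + 37.5 − 5 | 585.5 |
| Own tube | Own tube | 553 + 37.5 | 590.5 |

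**Step 7. Possible ceilings under 8.4.1.** These are 538.5 mL, 548 mL, 538.5 + 50 = 588.5 mL, and 548 + 50 = 598 mL. All four totals exceed 538.5 mL. Only 590.5 mL exceeds 588.5 mL, and none exceeds 598 mL.

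**A side condition.** Section 8.4.3 puts prolactin and leptin on Days −1 and 9, not at screening and Day 9. On that timing the extra screening tube falls away. Each total drops by 2.5 mL, giving a range of 545.5 to 588.0 mL, still above 538.5 mL.

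**The case against.** The strongest reply is that the certain part is small and the larger part conditional. That largely stands. The text and table differ by 1.8%. The OGTT draws are not absent from the table, since the biochemistry and glucose row must already hold at least 11 of them. Section 8.4.3 puts glucose and insulin in the same type of serum-separating tube, so one tube could serve both assays. If leptin is also shared, the 5 mL saved offsets the 5 mL shortfall and the corrected total is exactly the printed 548 mL.

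Against this, at the profile times the table charges an insulin tube as well as a biochemistry and glucose tube, and the biochemistry row does not name insulin. The same convention at the OGTT times would require 37.5 mL that the table lacks. The documents do not settle the point.

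A reader might infer three stronger things that the documents do not support:

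- **That every completer breaches the limit, or samples must be dropped.** The 8.4.1 sentence qualifies permission to add or change time points; it does not tell the site to omit planned samples. The value it points to could be any of four figures, and correcting the number resolves the conflict.
- **That planned sampling exceeds even the 50 mL allowance.** This needs separate tubes for both OGTT insulin and leptin, the schedule's screening sample, and 538.5 mL as the base. The allowance is itself worded for additional emodepside, metabolite and safety assays, so it does not clearly cover planned OGTT samples either.
- **That subjects or the ethics committee were told 538.5 mL.** The documents available do not show the consent form's figure, and the protocol prints both numbers.

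**Conclusion.** The point holds and the text is wrong as written. Two elements need no assumption about tubes: the stated total is 9.5 mL below the table's correct sum, and 8.4.1 refers to a section with two totals and a separate allowance, so the ceiling is not identifiable. The biochemistry and glucose row is short by two tubes (5 mL) even with full sharing at coinciding times.

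The remaining discrepancy depends on tube sharing. On the schedule's timing and with coinciding samples shared, the total lies between 548 and 590.5 mL. That is 9.5 to 52 mL above the stated figure (590.5 − 538.5 = 52). The upper end should not be quoted without its conditions. The consequence is an unclear limit on blood drawn, which should be corrected; the trial's objectives, sample size and analyses are untouched.

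**What to change.** In protocol 8.4.4:

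1. Recount every row from the schedule footnotes and correct the biochemistry and glucose row from 40 to 42.
2. State whether OGTT insulin is assayed from the glucose tube and whether leptin is taken from the insulin tube, and set those rows to match. Reconcile the prolactin and leptin days in 8.4.3 with the schedule at the same time.
3. Print the same total in the text and the table.

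In 8.4.1, give the ceiling in mL and say whether it includes the 50 mL allowance. Check any subject-facing figure against the corrected total.

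The cost is a small text amendment and a stated volume at least 9.5 mL higher on the schedule's timing. No sample is added or removed.
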